# 7.3. Lost to Follow up

A participant will be considered lost to follow-up if the participant repeatedly fails to return for scheduled visits or is unable to be contacted by the study site.

The following actions must be taken if a participant fails to return to the clinic for a required study visit:

The site must attempt to contact the participant and reschedule the missed visit as soon as
possible, counsel the participant on the importance of maintaining the assigned visit
schedule, and ascertain whether the participant wishes to and/or should continue in the
study.

© 2015-2021 TransCelerate BioPharma

Doc. No. CT 2.01.01. Valid from 31 Jan 2022.

Only the electronic version is valid.

Page 28 of 65

# CONFIDENTIAL The CORTAD study Clinical Trial Protocol version6.2, 15thNovember 2023

- Before a participant is deemed lost to follow-up, the investigator or designee must make
  every effort to regain contact with the participant (where possible, telephone calls, and if
  necessary, a certified letter to the participant's last known mailing address or local
  equivalent methods). These contact attempts should be documented in the participant's
  medical record.
- Should the participant continue to be unreachable, the participant will be considered to have withdrawn from the study.

© 2015-2021 TransCelerate BioPharma

Doc. No. CT 2.01.01. Valid from 31 Jan 2022. Only the electronic version is valid.

Page 29 of 65

# 8. Study Assessments and Procedures

- Study procedures and their timing are summarized in the SoA (for time line se figure on page 22). eCRF forms are generated using the Fasttrack infrastructure and is available in Endojournal and Noklus Diabetes at every hospital, one form per visit (visits 1-6). Protocol waivers or exemptions are not allowed.
- Adherence to the study design requirements, including those specified in the SoA, is essential and required for study conduct.
- All screening evaluations must be completed and reviewed to confirm that potential
  participants meet all eligibility criteria. The investigator will maintain a screening log to
  record details of all participants screened and to confirm eligibility or record reasons for
  screening failure, as applicable.
- Procedures conducted as part of the participant's routine clinical management (ie, hormone levels at diagnosis, 21-OH autoantibodies, blood count, renal function, glucose, electrolytes, lipids) obtained before signing of the ICF may be utilized for screening or baseline purposes provided the procedures met the protocol-specified criteria and were performed within the timeframe defined in the SoA.
- In the event of a significant study-continuity issue (e.g., caused by a pandemic), alternate strategies for participant visits, assessments, medication distribution and monitoring may be implemented by the sponsor or the investigator, as per local health authority/ethics requirements.

The maximum amount of blood collected from each participant over the duration of the study, including any extra assessments that may be required, will not exceed 500 mL.

Repeat or unscheduled samples may be taken for safety reasons or for technical issues with the samples.

### 8.1. Administrative Procedures

### 8.1.1. Screening visit (Visit 1)

No study related procedures must be performed before the patient has been informed about the study and the informed consent form is signed and dated by both the patient and the investigator, according to procedure described in section 10.1.3.

Exceptions: procedures conducted as part of the participant's routine clinical management (ie, hormone levels at diagnosis, 21-OH autoantibodies, blood count, renal function, glucose, electrolytes, lipids) and obtained before signing of the ICF may be utilized for screening or baseline purposes provided the procedures meet the protocol-specified criteria and were performed within the timeframe defined in the SoA.

For simplification, tasks for the recruiting physician at visits 1 and 2 are summarized below:

© 2015-2021 TransCelerate BioPharma

Doc. No. CT 2.01.01. Valid from 31 Jan 2022.

Only the electronic version is valid.

Page 30 of 65

### Screening, Inclusion and Randomisation (tasks for the recruiting physician)

- Provide information and ensure signed informed consent (stored on paper).
- Fill inn study form in Noklus diabetes (Fasttrack).
- Etiology of PAI: Determine 21-hydroxylase autoantibodies to secure diagnosis of autoimmune PAI. In antibody-negative patients: a computer tomography of the adrenal region is required to look for tumour, bleeding, or infections, or known bilateral adrenalectomy.
- Regular blood chemistry including hemoglobin, erythrocyte volume fraction, leucocytes, thrombocytes, creatinine, Na, K, calcium, magnesium, and alanine amino transferase and lipids (if not already done).
- Screening for common endocrine co-morbidities is performed:
  - Autoimmune thyroid disease: TSH, FT4, anti-thyroperoxidase, anti TSH-receptor autoantibodies.
  - Autoimmune gastritis: cobalamin, ferritin, methyl malonic acid, parietal cell antibodies and intrinsic factor autoantibodies.
  - Type 1 diabetes: HbA1c.
  - Celiac disease: transglutaminase-2 autoantibodies.
- Serum, EDTA blood (DNA), urine (steroid metabolome), and hair sample (cortisol) for biobanking
- Clinical examination including, height, weight, waist circumference, blood pressure (standard protocol) sitting and standing. Please note pigmentation, signs of vitiligo or alopecia, menstruation (menarche, menopause) in women.
- HRQoL questionnaires (AddiQoL and RAND-36)
- Randomization to either Cortisone or Plenadren.
- Education in stress dosing, sick-day rules, self-injection of hydrocortisone, and issuing of steroid card.
- Submit prescription to pharmacy.
- Register diagnosis in the summary care record ("Kjernejournal").
- Schedule blood sampling 1 and 4 hours after intake of GC replacement morning dose for evaluation and adjusting of the dosage at Visit 3.
- Cognitive testing

© 2015-2021 TransCelerate BioPharma

Doc. No. CT 2.01.01. Valid from 31 Jan 2022.

Only the electronic version is valid.

Page 31 of 65

### 8.1.2. Randomization and Baseline visit (Visit 2)

Randomization to either Cortisone or Plenadren can be done after screening and attaining an informed consent, either before or at visit 2 (day 0). The including investigator will the study nurse at HUH on a dedicated phone number and the consenting participant will be randomized to either treatment type. Randomization will be performed centrally and in blocks of four to secure equal assignment number in each group. A prescription for the study drug including recommended dosage will thereafter be provided to the patient.

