# CONFIDENTIAL The CORTAD study Clinical Trial Protocol version6.2, 15thNovember 2023

Procedure	ng ation			Intervention Period				
	Screening	Randomization	Baseline	Phone visit	Lab visit			
Visit number	1		2	3	4	5	6	7
Diagnostic laboratory tests adrenal insufficiency 	X							
Laboratory tests (hematology, electrolytes, creatine, liver enzymes, cholesterols and triglycerides, HbA1c, cobalamine, , ferritin, renin, aldosterone, 25OH vitamin D, TSH, FT4)			X			X	X	
HOMA index (insulin and glucose)			X			X	X	
Serum and EDTA samples for Biobanking forc- peptide, bone markers, BDNF, metylmalomic acid and autoantibody screening (etiology and autoimmune comorbidity)			X			X	X	
Urine sample (steroid metabolome)							X	
Hair sample (cortisol)			X				X	
HRQoL questionnaires (RAND-36, AddiQoL-30)			X		X	X	X	
Cognitive tests	X					X	X	
Bone mineral density and body composition					X		X	
Blood sampling 1 and 4 h after morning dose (S-cortisol)					X			
Dose adjustment according to S-cortisol (if applicable) 					X			
Saliva cortisol (before, +1h and +4 h after morning dose						X	X	

© 2015-2021 TransCelerate BioPharma

Doc. No. CT 2.01.01. Valid from 31 Jan 2022.

Only the electronic version is valid.

Page 12 of 65

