### 6.4. Blinding, Masking

This is an open-label study; potential bias will be reduced by central randomization.

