### **8.2.1.** Patient Reported Outcome (PROMs)

- Two HRQoL will be sampled at baseline and after 1, 6 and 12 months; the generic questionnaire RAND-36 and the PAI-specific questionnaire AddiQoL. RAND-36 is thoroughly validated and extensively used and suitable both for comparison of HRQoL scores between PAI and healthy controls, and for comparing score between PAI and other disease groups (20). The AddiQoL is developed and thoroughly validated by us as a PAI-specific HRQoL instrument, more sensitive for detecting changes in HRQoL over time in PAI (21).
- For evaluation of sleep, Sleep Diary will be sampled at visit 5-6.
- Working ability (i.e. sick leave, sick pension) will be registered at each visit (NOKLUS study form).
- Cognitive test administration using Memoro, a web-based cognitive test platform developed by [name] and [name], NTNU (28-30). The test can be run on a computer, tablet, or smartphone. Participants receive links via sms, e-mail, as a printed pdf (letter) or through helsenorge.no. Memoro uses same encryption as online banking (nettbanken) and has ROS analysis approving the system. The server is located at NTNU's central server location. No clinical data is stored only the test scores. Some background variables are stored to provide norm data for references (year born, education level according to groups (vgs., bachelor, master or above) and handedness). Participants can receive their scores relative to the norm data if that is of interest. Score will be transferred directly to TSD or similar server at UiT/Haukeland or via encrypted file sender. The cognitive tests that will be used have been used in many other studies (incl. HUNT and MoBa) and have therefore system norms as a reference.

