## 9.1. Statistical Hypotheses

Table 4 includes all objectives with corresponding hypothesis and statistical analyses.			
Number	Objective	Hypotheses	Statistical analysis
	Primary		
1.1	Is improvement of HRQoL in PAI patients treated with Plenadren better than improvement of HRQoL in PAI patients treated with Cortisone after 6 and 12 months?	Null hypothesis:  H 0 : $P_{Plen(0-12)} = P_{Cort(0-12)}$ Alternative hypothesis:  H 1 : $P_{Plen0-12} \neq P_{Cort0-12}$ $P_{Plen (0-12)}$ : Increase in HRQoL score from Baseline to 6 and 12 months in Plenadrentreated patients $P_{Cort(0-12)}$ : Increase in HRQoL score from Baseline to 6 and 12 months in Cortisontreated patients	Between group comparison of longitudinal change in HRQoL score by linear mixed effect models for repeated measures.
	Secondary		
2.1	Is there a between group difference in clinical markers of cardio-metabolic health between patients receiving Plenadren and conventional thrice daily Cortisone for 12 months?	Null hypotheses: There is no difference in clinical markers of cardio-metabolic health between patients receiving Plenadren and	Comparing between-group clinical characteristics (BP, BW, BWC, BMI), lipids, glucose and HOMA index between Plenadren-treated and Cortison-treated patients.

© 2015-2021 TransCelerate BioPharma

Doc. No. CT 2.01.01. Valid from 31 Jan 2022.

Only the electronic version is valid.

Page 42 of 65

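### The baseline of the primary HRQoL endpoint may be scored after the allocation is known, because randomisation is allowed before visit 2 and nothing requires the questionnaires to come first

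*Protocol*

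**What the plan says.** **Timing of randomisation.** Protocol Section 8.1.2: "Randomization to either Cortisone or Plenadren can be done after screening and attaining an informed consent, either before or at visit 2 (day 0". It continues: "A prescription for the study drug including recommended dosage will thereafter be provided to the patient". The Schedule of Activities (Section 1.3) has a Randomization column between Screening (day -31 to 0) and Baseline (visit 2, day 0).

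**Timing of the baseline questionnaires.** In the same schedule the row "HRQoL questionnaires (RAND-36, AddiQoL-30") has its first mark under Baseline and none under Screening or Randomization. Section 8.2.1 agrees: "Two HRQoL will be sampled at baseline and after 1, 6 and 12 months".

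**Task list.** Section 8.1.1 gives the recruiting physician a combined list for visits 1 and 2. The item "HRQoL questionnaires (AddiQoL and RAND-36") stands on the line directly above randomisation. Cognitive testing stands last, although the Schedule of Activities marks the first cognitive test at Screening.

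**Blinding.** Section 6.4: "This is an open-label study; potential bias will be reduced by central randomization".

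**Primary analysis.** Section 9.1 defines the compared quantity as "Increase in HRQoL score from Baseline to 6 and 12 months" in each arm, analysed as "Between group comparison of longitudinal change in HRQoL score by linear mixed effect models for repeated measures".

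**The concern.** In an open-label trial with a self-reported primary outcome, the baseline score is the one HRQoL measurement that can be kept free of knowledge of the arm. That requires it to be taken before the allocation is released, and the protocol does not ask for this. Central randomisation, the safeguard named in Section 6.4, protects concealment up to the moment of assignment. It does nothing about how a patient answers a questionnaire afterwards.

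Expectation is plausible here. Sections 2 and 4.2.1 refer to a prevailing view that Plenadren is the better, more physiological replacement. The remedy in Sections 2.1 and 4.1, enrolling only newly diagnosed patients, addresses comparison with an earlier treatment. It does not address a patient's reaction to the arm drawn.

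Because baseline enters the primary estimate, any arm-related shift in it enters the treatment comparison. No later analysis can reliably remove a shift whose size and direction were not observed, so this has to be settled in the visit procedures.

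**Working it through.** **1. Reading the sections together**

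| Place | What it fixes |
|---|---|
| 8.1.2 | Randomisation allowed before visit 2; prescription follows it |
| 1.3 (schedule) | Screening up to 31 days before day 0; first HRQoL mark at visit 2 |
| 8.2.1 | HRQoL at baseline, 1, 6 and 12 months |
| 8.1.1 (task list) | Questionnaires listed just above randomisation; order not stated as a rule |
| 6.4 | Open label; central randomisation the only measure named |
| 9.1 | Primary quantity is change from baseline |

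A site following 8.1.2 and the schedule to the letter may randomise first and collect the baseline questionnaires later. The same can happen within visit 2 if the call precedes the forms. No section forbids either.

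**2. The plan's own figure**

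Section 9.3 assumes a difference of 4 and SD of 4 in AddiQoL, two-sided 5% and 90% power, giving 21 per group.
- (1.960 + 1.282)² = 10.51, and 2 × (4/4)² × 10.51 = 21.01 per group. Normal-approximation power at 21 per group is 90.0%.
- The stated 21 is thus reproduced to within rounding. The printed constant of 10.9 would give 21.8; that is a separate matter and does not affect this point.

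**3. How a baseline shift enters the estimate**

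Let b be the between-arm difference in mean baseline score caused by knowing the arm, averaged over all patients, and f the corresponding difference at follow-up.
- Change score: bias = f − b.
- Model adjusting for baseline with slope s: bias = f − s × b.

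The documents give no value for b or f. **The values of b below are assumptions for illustration, with f set to 0.**
- Change score: bias of 0.5 to 2 points in size. Against the target of 4, that is 0.5/4 = 12.5% to 2/4 = 50%.
- Baseline-adjusted, with assumed slopes 0.3 to 0.7: 0.5 × 0.3 = 0.15 to 2 × 0.7 = 1.4 points.

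**4. What that would do to the test**

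Taking SD 4 for the analysed difference and 21 per arm, the standard error is 4 × √(2/21) = 1.23. The rejection probability is 1 − Φ(1.96 − δ/1.23) + Φ(−1.96 − δ/1.23), where δ is the bias when there is no true difference, or the true difference less the bias.

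| Assumed b | Type I error, full carry-over | Type I error, half carry-over | Power at true difference 4, full carry-over against the effect |
|---|---|---|---|
| 0 | 5.0% | 5.0% | 90% |
| 0.5 | 6.9% | 5.5% | 81% |
| 1 | 12.8% | 6.9% | 68% |
| 1.5 | 22.9% | 9.3% | 53% |
| 2 | 36.7% | 12.8% | 37% |

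These figures show sensitivity only. If only some patients score baseline after learning the arm, b shrinks in proportion.

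**The case against.** **The task list already has the right order.** A physician working down Section 8.1.1 would collect the questionnaires before randomising. This stands as mitigation. But the list is introduced as a simplification covering two visits, it is not reliably chronological (cognitive testing comes last, against the schedule), and it cannot override the explicit permission in 8.1.2.

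**An early call is not early disclosure.** Section 8.1.2 gives no date for the prescription, and the schedule marks its submission to the pharmacy at Baseline. No section says the patient is told at the time of an early call, and the 31 days are only an outer limit. This also stands: disclosure before the questionnaires is possible, not scheduled.

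**Net bias is not isolated.** Patients know their arm at 1, 6 and 12 months in any case. If expectation moves baseline and follow-up the same way, f and b partly cancel in the change score. This stands too, and it is why the illustration cannot be read as an estimate. It does not justify the present wording, since an unplanned and unmeasured offset is no safeguard.

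A reader might infer that the design places baseline after allocation, or that the primary result is biased by 12.5% to 50% of the target. The documents support neither. The wording permits the worse order without prescribing it, and no figure in the documents anchors the shift.

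**Conclusion.** The point holds as a permitted and avoidable risk. Sections 8.1.2 and 1.3 together allow the baseline of the primary change-from-baseline endpoint to be scored after the patient has learned the allocation, and the only text pointing the other way is a non-binding list.

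That much is certain from the text. That a bias will arise is not: it depends on how often randomisation precedes the questionnaires, whether the patient is told, whether knowledge of the arm alters the answers, and how far follow-up scores move the same way. The 0.5 to 2 point illustration rests on an assumed shift with follow-up unaffected.

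The change should be made because the order cannot be repaired once the data are in and correcting it costs almost nothing. It would not remove the open-label influence on follow-up scores, and it has no bearing on the sample size.

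**What to change.** - **Section 8.1.2:** state that AddiQoL-30, RAND-36 and the baseline cognitive test must be completed and dated before the randomisation call.
- **Randomisation call:** have the study nurse at the central site confirm completion before releasing the allocation.
- **Schedule of Activities:** add a footnote to that effect, or move the first HRQoL mark to a column before Randomization. Changing the order of the rows would do nothing, because timing is set by the columns. The cognitive test is already marked at Screening and needs only the footnote.
- **Section 8.1.1 task list:** keep the questionnaires ahead of randomisation, say that this order is required, and move cognitive testing ahead of randomisation so that it agrees with the schedule.
- **Participants already randomised:** record from the available dates whether the questionnaires preceded the call.

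The cost is one sentence, one footnote and one check item in a call that already takes place. No extra visit, questionnaire or participant is needed, and treatment is unchanged.

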### 8.1.3. Follow-up visits

### Visit 3 – Telephone visit 1 week after inclusion

• Physician/ nurse: Interview the patient on the effect of the medication by filling out the adrenal insufficiency form in Noklus Diabetes.

### Visit 4 - 1 month

- Physician/ nurse: Interview the patient on the effect of the medication by filling out the adrenal insufficiency form in Noklus Diabetes.
- Patient: Fill in PROMS, including HRQoL questionnaires.
- Note any side-effects, adrenal crisis, infections, or any new concomitant disease and their treatment.
- Blood sampling is performed for serum cortisol 1 and 4 hours after intake of GC replacement morning dose for evaluation and adjusting of the dosage.
- Bone mineral density measurement, body composition, and measure bone markers as well as vitamin D.

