### 1.2. Schema

Potentially eligible study participants are all newly diagnosed patients with primary adrenal insufficiency (PAI). The diagnostic criteria are basal serum cortisol < 100 nmol/L combined with p-ACTH > 2 x upper reference limit: or synacthen—stimulated serum cortisol < 485 and p-ACTH > 2 x upper reference limit.

In patients randomized to conventional Cortisone, the initial replacement dosage will be 25 mg divided in three doses according to current clinical routine. Patients randomized to Plenadren will receive an initial dosage of 20 mg, as in previous clinical trials (17). One week after inclusion and treatment initiation, the patient will return for blood tests for evaluation and individual adjustment of the dosage.

The Section of Endocrinology at The Department of Medicine at Haukeland University Hospital (HUH) and The Endocrine Medicine Group at Department of Clinical Science at the University of Bergen (UiB) have built up a unit for translational research in endocrinology. The outpatient clinic is staffed with experienced personnel in handling patients and samples. The Fasttrack infrastructure to be used for registration of study information, is well established and used for all outpatient contacts at Section of endocrinology, Department of Medicine, Haukeland University Hospital. The system is available at all hospitals in Norway through Noklus Diabetes and can be used by the network of dedicated physicians. It has recently been used in clinical studies (27), and proven to be a safe, robust and efficient way to register study information. An array of autoantibody assays are available, including 21-hydroxylase autoantibodies. The core facility for

© 2015-2021 TransCelerate BioPharma

Doc. No. CT 2.01.01. Valid from 31 Jan 2022. Only the electronic version is valid.

Page 9 of 65

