### 6.6. Dose Modification

Participants will start on either 20 mg Plenadren once daily or 25 mg Cortisone divided in three daily doses. The Cortisone tablet can be divided into halves or quarters so that one half is given in the morning, a quarter at midday and a quarter in the afternoon (12.5 + 6.25 + 6.25 mg daily). Any dose modification can be made at the discretion of the study investigators. The study protocol includes measurement and cortisol in saliva and serum to aid clinicians in dose modification. Likewise we have developed ten clinical questions for the patients to clarify symptoms that may indicate a need for dose adjustment.

After one week serum cortisol will be sampled one and four hours after ingesting the morning dose to assess drug uptake. If a dose change is deemed necessary based on these results and clinical evaluation of the patient, the doses will be altered if necessary, and documented in the study files. If the patient develops symptoms and/or signs of overtreatment with glucocorticoid (unexpected weight gain, Cushingoid clinical signs), a dose reduction will be instituted at the investigators discretion, normally a 25% reduction in daily dose. Accordingly, if the patient has symptoms of undertreatment (i.e. debilitating fatigue, increased pigmentation) and post dose serum cortisol levels are low, a dose increase will be instituted at the investigators discretion, normally a 25% increase in daily dose.

© 2015-2021 TransCelerate BioPharma

Doc. No. CT 2.01.01. Valid from 31 Jan 2022. Only

Only the electronic version is valid.

Page 26 of 65

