#### **8.3.3.** Clinical Safety Laboratory Tests

• See the SoA (Section 1.3) for the timing and frequency of laboratory tests.

© 2015-2021 TransCelerate BioPharma

Doc. No. CT 2.01.01. Valid from 31 Jan 2022.

Only the electronic version is valid.

Page 37 of 65

• To assess dose safety, serum cortisol will be measured 1 and 4 hours after the participant has administered the morning dose between visit 2 and 3. If a dose increase or decrease is deemed necessary, cortisol measurement 1 and 4 hours after the participant has administered the morning dose will be repeated after one week.

Table 8.3.3. Laboratory parameters for PAI diagnosis at screening (blood, serum, plasma)			
Hematology			
Hemoglobin	Platelet count / thrombocytes		
WBC/leukocytes			
Lipids			
Cholesterol	• LDL		
• HDL			
	
 
Triglycerides
 
		
Clinical chemistry			
• HbA1c	
 
Potassium
 
		
• Glucose	
 
Sodium
 
		
Creatinine	
 
Calcium
 
		
Ferritin	
 
Albumin
 
		
	
 
Cobalamin
 
		
Hormones			
TSH (thyroid stimulating hormone)	• Renin		
• Free T4	
 
Aldosterone
 
		
	
 
Cortisol
 
		
TPO antibodies	• ACTH		
	
 
DHEAS
 
		
• 21-OH antibodies			

- The investigator must review the laboratory results, document this review, and record any clinically significant changes occurring during the study as an AE. The laboratory results must be retained with source documents.
- Abnormal laboratory findings associated with the underlying disease are not considered clinically significant unless judged by the investigator to be more severe than expected for the participant's condition.
- All laboratory tests with values considered clinically significantly abnormal during
  participation in the study should be repeated until the values return to normal or baseline
  or are no longer considered clinically significant by the investigator or medical monitor.

© 2015-2021 TransCelerate BioPharma

Doc. No. CT 2.01.01. Valid from 31 Jan 2022.

Only the electronic version is valid.

Page 38 of 65

- [If clinically significant/any] values do not return to normal/baseline within a period of time judged reasonable by the investigator, the etiology should be identified, and the sponsor notified.
- All protocol-required laboratory tests must be conducted in accordance with the laboratory manual and the SoA (Section 1.3).

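### The week-1 post-dose serum cortisol check required in the text is missing from the schedule of activities, which places it only at day 28

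*Protocol*

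**What the plan says.** Five sections of the Protocol point to week 1.

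- Section 1.2 (Schema): "One week after inclusion and treatment initiation, the patient will return for blood tests for evaluation and individual adjustment of the dosage". Section 4.3 repeats the sentence and gives the purpose of the 1-hour and 4-hour cortisol: to pick up marked overdosing or failure to absorb the drug.
- Section 6.6 (Dose Modification): "After one week serum cortisol will be sampled one and four hours after ingesting the morning dose to assess drug uptake".
- Section 8.1.1 (tasks for the recruiting physician): "Schedule blood sampling 1 and 4 hours after intake of GC replacement morning dose for evaluation and adjusting of the dosage at Visit 3".
- Section 8.3.3 (Clinical Safety Laboratory Tests) gives dose safety as the reason for this sample, and its wording on timing is "administered the morning dose between visit 2 and 3". If the dose is then changed, the measurement is to be repeated a week later.

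Two places point to day 28 only.

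- The SoA (section 1.3) has one mark in the row for the post-dose serum cortisol and one in the row for the cortisol-based dose adjustment. Both are in the visit 4 column. Visit 3, at day 7, is headed as a phone visit.
- Section 8.1.3 describes visit 3 as a telephone interview at one week with no blood draw. Under visit 4, at one month, it says: "Blood sampling is performed for serum cortisol 1 and 4 hours after intake of GC replacement morning dose for evaluation and adjusting of the dosage".

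On which source sets laboratory timing, section 8.3.3 says: "See the SoA (Section 1.3) for the timing and frequency of laboratory tests". It also requires protocol laboratory tests to follow the laboratory manual and the SoA. Section 8 treats adherence to design requirements, the SoA's among them, as essential.

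**The concern.** The same sample, with the same purpose, is placed at about one week in some sections and at one month in others, and no sentence reconciles them. Section 8.3.3 contradicts itself in effect: it requires a sample between visits 2 and 3, and refers the site for timing to a schedule that has no such sample. Section 8.1.1 asks for blood sampling at visit 3, which the SoA and 8.1.3 both make a telephone contact.

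The protocol itself classes the sample as a dose-safety check. The participants are newly diagnosed, depend on glucocorticoid replacement for survival (section 2.2), and start on a fixed dose that is then adjusted individually. A site working from the SoA and the visit descriptions could leave out the first check without noticing that it had departed from the protocol. Patients are recruited across Norway by investigators who telephone the central site for randomization (sections 5 and 6.3), so different readings at different sites are a realistic possibility.

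**Working it through.** The plan gives no figure to reproduce. The check is a comparison of the stated times, plus a subtraction.

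**Reading the SoA columns.** In order, the columns are visit 1, randomization, visit 2 (day 0), visit 3 (phone visit, day 7), visit 4 (lab visit, day 28), visit 5 (day 182), visit 6 (day 365) and visit 7. The single mark in the post-dose cortisol row, and the single mark in the dose-adjustment row, fall in the fifth of these columns, which is visit 4. Because the table was extracted from PDF, the alignment was tested on rows whose timing is also given in prose:

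- The quality-of-life row, read the same way, falls at visits 2, 4, 5 and 6. Section 8.2.1 gives baseline and 1, 6 and 12 months.
- The bone density row falls at visits 4 and 6. Section 8.1.3 lists that measurement at visits 4 and 6.

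Section 8.1.3 also gives the same cortisol timing in words, so the day-28 reading does not depend on the table alone.

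**The statements side by side.**

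| Protocol section | Timing given | Names the 1 h/4 h cortisol at that time? |
|---|---|---|
| 1.2 | one week, patient returns | blood tests only |
| 4.3 | one week, patient returns | blood tests at one week; the 1 h/4 h cortisol is named separately, without a day |
| 6.6 | after one week | yes |
| 8.1.1 | visit 3 (day 7) | yes |
| 8.3.3 | between visits 2 and 3 (days 0 to 7) | yes |
| 1.3 (SoA) | visit 4 (day 28) only | yes |
| 8.1.3 | visit 4 (one month) only; visit 3 by telephone | yes |

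**Size of the gap.** First scheduled biochemical check on the SoA reading minus that on the text reading: 28 − 7 = 21 days. Section 8.3.3 allows the sample earlier than day 7, so 21 days is the minimum. The gap is 21/28 = 75% of the first 28 days. This measures calendar time, not risk.

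**Knock-on for the repeat sample.** Section 8.3.3 asks for a repeat one week after a dose change. If the dose is changed on the day of the first sample, the repeat falls at about 7 + 7 = day 14 on the text reading and 28 + 7 = day 35 on the SoA reading.

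**Could the day-28 sample be the repeat?** No. The repeat is conditional on a dose change and follows it by a week. The visit 4 sample is listed for everyone.

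**The case against.** The strongest reply is that the two sets of statements are compatible. A site can draw blood in week 1 and again at visit 4, and no sentence says that only one sample is meant. On that reading the defect is an omission from the SoA and from the visit 3 description, not a contradiction. This is possible, but the week-1 draw is still absent from the schedule that section 8.3.3 names for laboratory timing.

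A second reply is that the SoA does not override the text. Section 8 calls it a summary, its adherence sentence covers all design requirements, and 8.3.3 also refers to a laboratory manual that is not available here and may list the draw. This stands in part: nothing gives the SoA formal precedence. It also means nothing tells a site which source to follow.

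A third reply is that omission is unlikely and its consequences limited. The 8.1.1 task list tells the recruiting physician to arrange the week-1 sample. The day-7 call asks about the effect of the medication, and the SoA has dosing and compliance reviewed at that visit. Investigators may change doses at their discretion, and extra samples for safety are permitted. Both drugs are licensed and prescribed as in usual care, and section 4.3 has titration guided by a structured symptom history. All of this is correct and lowers both the chance and the cost of a missed sample. However, a symptom interview does not measure drug uptake, which is why section 6.6 asks for the sample.

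**Conclusion.** The point holds. The protocol requires a post-dose serum cortisol check in week 1 but does not schedule it there: the SoA and section 8.1.3 place it only at day 28. For a site relying on the SoA, the first scheduled biochemical check of the dose moves back by at least 21 days.

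That a site would actually omit the sample is an inference from the reference to the SoA for laboratory timing and from visit 3 being by telephone; the documents do not show it happening. The laboratory manual could not be checked. The conflict applies to both arms, and no effect on the primary quality-of-life comparison (hypothesis 1.1) is shown or claimed. It should be fixed because it leaves a dose-safety check ambiguous in patients who cannot do without treatment.

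**What to change.** 1. In the SoA, mark the 1-hour and 4-hour serum cortisol sample and the cortisol-based dose adjustment at week 1. Specify that blood is drawn by visit 3 and the result discussed at the visit 3 call.
2. Add the draw to the visit 3 description in section 8.1.3.
3. State in the SoA and in 8.1.3 whether the visit 4 sample is an additional routine check or is removed.
4. Check the wording of 1.2, 4.3, 6.6, 8.1.1 and 8.3.3 against this. They already point to week 1, so little should change beyond making clear that the draw is a laboratory attendance and not part of the call.

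Moving every section to visit 4 would also remove the inconsistency, but it would give up the early check that 6.6 and 8.3.3 ask for. If the sponsor prefers it, the protocol should say why.

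The cost is a protocol amendment and a letter to sites. Sites now following only the SoA would add one week-1 attendance with two timed samples, which the text already requires.
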